12/08/03

VIRAHEP- C STUDY PROTOCOL

VIRAHEP- C Summary

Major advances have been made over the last decade in the field of antiviral therapy for chronic hepatitis C. Combination therapy with interferon and ribavirin has improved virological sustained response rates to nearly 40% compared to only 10-15% for patients treated with interferon alone. Unfortunately, response to therapy is not uniformly favorable. Secondary analyses of large databases derived from clinical trials of various antiviral agents have suggested that there may be racial disparities in response to therapy for hepatitis C. Sustained response rates in African American patients appear to be significantly less than in Caucasian patients treated with the same regimens. However, these trials were not designed specifically to study race as a factor in response to therapy and very few African Americans have been included as study subjects, despite the high prevalence of hepatitis C in this population.

VIRAHEP-C is a multicenter, collaborative clinical trial, sponsored by NIDDK-NIH, designed to test the hypothesis that African Americans respond less well to antiviral therapy than Caucasian patients. A total of 400 patients, equally divided between African American and Caucasians, will be enrolled at eight clinical centers throughout the United States. All participants will be HCV genotype 1. Participants will be treated for 48 weeks with pegylated interferon alfa-2a 180 mcg/week plus ribavirin 1000-1200mg/day. Participants will be followed for an additional 48 weeks after cessation of therapy. Sustained virological response rates (undetectable HCV RNA in serum 24 weeks post-treatment) and durable sustained virological response rates (undetectable HCV RNA in serum 48 weeks post-treatment) between the two cohorts will be compared to determine differences in treatment response between the two racial groups.

Clinical and virological data from these treatment cohorts will be used to evaluate factors associated with resistance to antiviral therapy in African Americans and Caucasians with chronic hepatitis C. Pretreatment variables such as gender, history of alcohol use, HCV RNA levels, hepatic histology, among others, will be investigated to determine which factors may be associated with sustained virological response and how they may differ between racial groups.

Ancillary studies, using serum and peripheral blood mononuclear cells obtained from participants at various time points in this study, will be performed to investigate potential mechanisms of antiviral resistance. Thus, viral kinetics (the rate at which HCV RNA is cleared from serum during therapy), immunological responses, measures of interferon signaling pathways, and host and viral genetics will be evaluated in relationship to treatment response. This comprehensive study design that encompasses a clinical trial with prospective studies of mechanisms of antiviral resistance will be positioned to answer important clinical questions about the treatment of chronic hepatitis C.

1.0 Introduction

1.1 Background

Since the discovery of the hepatitis C virus (HCV) in 1989, there have been enormous advances in the understanding of the epidemiology, course, natural history and treatment of hepatitis C. In population-based surveys in the United States, 1.8% of Americans have been found to have antibody to hepatitis C (anti-HCV) and about three-fourths of these also have HCV RNA detectable in serum. ¹ These findings indicate that approximately 3.2 million Americans have been infected with HCV and 2.5 million have chronic infection. Many if not most patients with chronic hepatitis C are unaware of the presence of this virus or liver disease; nevertheless, HCV infection is an important cause of cirrhosis, end-stage liver disease and hepatocellular carcinoma. Hepatitis C is now the chief cause of hepatocellular carcinoma and the single major reason for liver transplantation in adults in the United States and most Western countries. ^{2,3,4}

The course and consequences of chronic hepatitis C have been defined in many natural history studies. The best estimates are that cirrhosis develops in 10% of HCV infected persons per decade. Thus, the life-time risk of developing cirrhosis is probably 20 to 50% depending upon the age of acquisition. Progression to cirrhosis is more frequent in males, in older individuals, and in those who drink alcohol to excess or are immunosuppressed.

Therapy of hepatitis C continues to evolve and now is successful in 40 to 50% of treated patients. ⁵ The regimen of therapy that yields the highest rate of response is the combination of alpha interferon and ribavirin. ^{6,7} The recent introduction of pegylated, long-acting forms of alpha interferon (peginterferon) promise to provide an even higher rate of response than with standard interferon. ⁸⁻¹⁰ In two large, randomized controlled trials, the combination of peginterferon and ribavirin for 48 weeks yielded overall sustained response rates of 54% to 56%. ¹⁰⁻¹² Retrospective analyses have repeatedly shown that responses to therapy are higher among persons infected with HCV genotypes 2 and 3 (66-82%) than those with genotype 1 (32-45%).

An important recent finding is that there are considerable racial differences in epidemiology, typical course, natural history and response to treatment of hepatitis C.¹³ The same population based surveys mentioned above demonstrated that African Americans have a higher rate of anti-HCV than Caucasians (3.2% vs. 1.8%) and a higher proportion have detectable HCV RNA (86% vs. 68%).^{1,13} These findings suggest that HCV infection is more common among African Americans than whites and that once infected, African Americans are also more likely to develop chronic infection. Findings from other cohort studies support these findings, but the reasons for these differences remain unknown.

The hepatitis C virus exists as at least six genotypes and several subtypes (1a, 1b, 2a, 2b, etc). Genotype 1 accounts for approximately 75% of HCV infections in the United States, genotype 2 for 10-15%, genotype 3 for 5-10%, and other genotypes and mixed infections for the remainder. The distribution of different genotypes in the United States also varies by race. Thus, genotype 1 affects 91% of African Americans compared to only 67% of whites. Genotype 1b is particularly more common among blacks (36%) than whites (18%) while genotype 3a is rare (<1% vs. 6%).¹³ Again the reasons for these differences are not clear. Furthermore, other racial groups, such as Hispanic whites and Asians in the United States, more closely resemble whites than African Americans in rates of chronicity and in genotype distribution.

Perhaps more significant than differences in prevalence, genotype, and outcome of hepatitis C between African Americans and whites, have been differences in response to antiviral therapy. A retrospective analysis of a randomized controlled trial of consensus interferon showed that both end-of-treatment and sustained biochemical and virological responses were less frequent in African Americans than whites with chronic hepatitis C.¹⁴ Specifically, only 5% (2 of 40) of black participants became HCV RNA negative by the end of therapy as compared to 33% (127 of 380) of white subjects. Sustained virological responses were also less common in African Americans, occurring in 12% (46 of 380) of white subjects, but in only 2% (1 of 40) of blacks. The differences appeared to be partially attributable to genotype differences, genotype 1 being more common among African American patients and also associated with a lower rate of virological response. Detailed analysis of changes in HCV RNA levels during therapy also showed racial differences. Median HCV RNA levels decreased to a lesser extent in black subjects than in whites (50% vs. 99.5%

reduction). Of note, in a logistic multiple regression model controlling for race, gender, baseline HCV RNA level and genotype (1 or not 1), the authors failed to demonstrate that either race or gender was associated with end of treatment or sustained virological response. The major reason for this lack of association in regression analyses may have been the few numbers of African Americans subjects, accounting for less than 5% of patients enrolled in this study.

Indeed, further analyses of several trials of antiviral therapy in chronic hepatitis C were limited because of the small number of African American subjects enrolled in these industry-sponsored studies. In large registration trials of interferon alfa-2a and alfa-2b, only 5% of enrolled subjects were black.¹³ For comparison, population based surveys suggest that African Americans represent 22% of cases of chronic hepatitis C. In a review of results from large clinical trials of interferon therapy of hepatitis C, only one African American patient was identified who had a sustained virological response to alpha interferon monotherapy.¹³

An important advance in therapy of hepatitis C was the demonstration that the addition of ribavirin to interferon therapy increased the response rate 2 to 3 fold. ^{6,7} This increase in response was due to both a higher rate of HCV RNA negativity during treatment and a lower rate of relapse when therapy was stopped. Retrospective analyses of trials of combination therapy have shown a lesser difference in response rates between black and white subjects. Thus, two large, multicenter trials have been conducted comparing 24 and 48 week courses of alpha interferon alone to the combination of alpha interferon and ribavirin in patients with chronic hepatitis C. Among 1744 subjects randomized, only 53 (2.6%) were black (because the studies were partially international, some of the blacks were not American).¹⁴ While 21% of white participants had a sustained virological response to alpha interferon monotherapy, none of 24 black subjects responded. With combination therapy, the overall response rate in blacks was 21% (6/28) which was considerably less than the 37% (346 of 925) response rate in whites. However, when controlled for by genotype, this difference was no longer statistically significant. Again, the small numbers of patients made it difficult to evaluate true differences. Repeated measures ANOVA were used to determine whether changes in serum HCV RNA levels during therapy varied by race. Compared to white subjects, black subjects had significantly less reduction in HCV RNA levels during therapy. This difference was most apparent in black subjects with genotype 1 infection who received interferon monotherapy. In multivariate analysis, race did not correlate with lack of virological response, but the few numbers of responses in black subjects (6 total) made the degree of accuracy poor.

The reasons for the lack of response to interferon therapy among African Americans are not clear. However, careful analyses of HCV RNA levels during therapy help define the degree of antiviral resistance. Monitoring HCV RNA during treatment shows several patterns of response including a "rapid" and "slow" responses in which levels fall to undetectable within a few weeks or months, as well as a "flat" and "nil" response in which HCV RNA levels fall by less than one log₁₀ or not at all. ^{13,15,16} In studies of small numbers of patients, it appears that flat and nil responses are more common among African Americans than whites. These types of studies suggest that one can identify patients who are non-responders within a few weeks or months of starting therapy and do not have to wait for 12 months of treatment and 6 of follow-up to identify subjects as resistant to current modes of antiviral therapy. These types of analysis provide important insights into the nature of antiviral responses and suggest many avenues for future studies.

1.2 Study Rationale

The lack of adequate studies of antiviral therapy of hepatitis C in African Americans and the preliminary results suggesting a lower response rate make it difficult to recommend therapy and provide estimates of risk and benefit in this population. Larger, well-designed prospective trials are needed to provide reliable and accurate information on response and adverse event rates as well as the role of predictive factors for response. If there is a lower rate of response among African American patients, analysis of factors that correlate with a lack of response may well provide insights into the nature of viral resistance and provide a basis for improving response rates.

For these reasons, we propose a prospective analysis of optimal combination therapy of hepatitis C in 200 African Americans and 200 white Americans with careful prospective analysis of features that may predict and elucidate non-response to treatment. For this study, we have selected the combination of pegylated interferon and ribavirin to be given for 48 weeks and have focused solely on patients with genotype 1, the

genotype with the lowest rate of response. In preparing this protocol, we have met with representatives of industry and have formed an agreement (CRADA) with the Hoffmann-La Roche pharmaceutical company to use their products: peginterferon alfa-2a (Pegasys) in a dose of 180 mcg weekly for 48 weeks and ribavirin in a dose of either 1000 mg (body weight less than 75 kilograms) or 1200 mg (body weight equal to or greater than 75 kilograms). The trial will include at least four ancillary studies of antiviral resistance, including special studies of viral genetics (HCV sequence and polymerase function), immunology (CD4 and CD8 responses to HCV antigens), host genetics (candidate gene polymorphisms done on lymphocyte DNA preparations), and interferon-signaling (induction of interferon responsive gene products during therapy).

2.0 Study Objectives and Endpoints

2.1 Specific Aims

1. To evaluate racial differences in response to antiviral therapy for chronic hepatitis C. Our hypothesis is that African Americans respond poorly to therapy for hepatitis C when compared to Caucasians with similar disease characteristics. Well-defined cohorts of African American and Caucasian patients with chronic hepatitis C (all genotype 1) will be treated with combination therapy (pegylated interferon and ribavirin) to determine differences in virological response rates between the two races.

2. Evaluate factors associated with resistance to antiviral therapy in African Americans and Caucasians with chronic hepatitis C. Pretreatment variables such as gender, history of alcohol use, HCV RNA levels, hepatic histology, among others, will be investigated to determine which factors may be associated with sustained virological response and how they may differ between racial groups. On-treatment variables will include viral kinetics, immunological responses, host response to interferon therapy, and adherence to therapy.

3. Evaluate differences in HCV viral kinetics in response to antiviral therapy and its relationship to sustained virological response. The rate of clearance from serum of HCV RNA will be compared between a cohort of African Americans and Caucasians to determine if racial differences exist, and between responders and non-responders to determine if they are predictive of treatment failure or success and if they are useful in the management of patients with chronic HCV.

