6.0 Data Analysis/Statistical Power

The study is designed to have 400 patients; 200 White/Caucasian, 200 Black/African American. There will be 80% power to detect a difference in the percentages of undetectable viral RNA 6 months following treatment (sustained virological response, SVR) between racial groups if the percentage of White/Caucasian patients with a SVR is 40% and the percentage in Black/African-American patients is 26% using a two-sided test with α = 0.05. In multivariable analyses, there will be 80% power to detect a difference if the percentages of SVR are 40% for Whites/Caucasians and 25% for Blacks/African Americans, assuming a multiple correlation coefficient of 0.4 between race and the other independent variables using a two-sided test with α = 0.05.

Primary analyses will be performed using all enrolled patients. Patients will be considered enrolled in the study upon taking the first dose of study medication. Participants who do not have outcome data will be included as treatment failures. We will also perform analyses that include only those participants with known outcome data.

Summary statistics will be generated to describe the study sample at baseline. Descriptive statistics, including measures of central tendency (e.g. means, medians) and estimates of spread (e.g., standard deviations) will be used for continuous variables such as age. Frequency distributions will be used for categorical variables such as education level. Ninety-five percent confidence intervals will be calculated for all point estimates of continuous data. Graphical displays (e.g. histograms, box plots) will also be used to describe the data. The baseline demographic information and viral characteristics of the racial groups will be compared using the chi-square test for association or exact tests for differences in proportions or trend in ordinal data. Continuous variables may be transformed, where appropriate, to meet the assumptions of parametric tests. The Student's t-test or a non-parametric alternative, the Wilcoxon rank-sum test, will be used to determine differences in the distribution of continuous data between the two racial groups.

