The proportion of African Americans and Caucasians with SVR will be compared using the chi-square test of association. The association between race and SVR after adjusting for potential confounders such as adherence, HCV sub-genotype, initial viral level, ALT, body mass index, and baseline histology will be assessed through multiple logistic regression analyses. The Hosmer-Lemeshow statistic will be calculated to determine if there is evidence that the final multiple logistic regression model does not fit. ²³ These

analyses will be repeated for durable viral response, i.e., having undetectable viral RNA 12 months following treatment discontinuation.

Generalized estimating equation (GEE) methods of Zeger and Liang.^{24,25} will be used to assess the differences between the racial groups with respect to changes in serum HCV RNA levels during therapy. This approach models both the regression of the response variable on the independent variables and accounts for the correlated nature of the responses. Analyses using conventional regression methods could provide erroneous variance estimates and loss of statistical efficiency because of the conventional assumption that each response is statistically independent. As a result, invalid inferences could be made if the conventional approach were applied to these longitudinal data.

The models examining response to treatment will include measures of adherence. As an initial step in examining adherence, graphical displays of the dosing history of each participant will be plotted and compared to the prescribed dosing regimen. Graphs include chronological plots showing the date and time of dose intake and frequency histograms of inter-dose intervals. The inter-dose interval representing the length of time between two successive doses will be calculated. For ribavirin, the optimal inter-dose interval is 12 hours and for peginterferon it is 7 days. Longer dosing intervals represent non-adherence and times in which the participant theoretically did not have adequate inhibitory drug concentration. In addition, summary statistics of adherence such as the percentage of prescribed doses taken and the percentage of drug holidays will be derived from the MEMS cap data. GEEs with multiple responses and adherence as a time-dependent covariate will be examined.

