Additional 400 anti-HCV positive viremic patients from an external (to Virahep-C) NIDDK source. To further increase the study's power, and serve as an important control group, 50 anti-HCV positive non-viremic (resolved infection) patients obtained from [name] (Principal Investigator, Immunology Study, Portland VA Medical Center) will be tested. A separate consent form for genetic studies will be obtained from participants (See Appendix 4). Refusal to participate in the genetics study will not exclude patients from participating in the treatment trial or other ancillary studies.

Method for Analysis/Power Calculations:

To test the association between response to therapy and genetic markers, we will compare the response rate among different genotypic groups or between carriers and non-carriers. A Chi-square or exact test, or a Mantel-Haenszel test when data are stratified across levels of a potentially confounding factor, will be used to test association between genotype and phenotype. For quantitative phenotype (e.g. reduction of viral levels since the treatment), we will compare the mean difference or percent change between each genotype group (homozygous for allele 1, heterozygous, and homozygous for allele 2) or the allele carrier and the noncarrier groups. A one-way ANOVA or two-sample t-test (or a non-parametric equivalent, e.g., Wilcoxon's rank sum test) will be used to test the associations between genotype and phenotype. The tests we use will depend on the allele frequencies, trait distribution, and sample size in each group. If an allele's frequency is low, e.g. 10%, we may not have enough homozygotes for that allele, and as a result the comparison will be between two groups (carrier and non-carrier). If preliminary analysis indicates potential confounding, analysis of covariance, Mantel-Haenszel Chi-square statistics, or multiple logistic regression will be used to control for confounding. Since Caucasians and African Americans have different response rates to interferon/ribavirin therapy, the effect of each specific gene may be not be the same in these racial groups. Thus, we will first analyze data separately within each racial group. Subsequent analyses will be based on all subjects by either combining results from stratified analysis (Mantel-Haenszel Chi-square test) or through adjustment for race in multivariable modeling (e.g., multiple logistic regression).

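### Aim 2 asks how predictors of SVR differ between races, but no analysis stated in the protocol compares a factor's association with SVR between the two groups

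*Protocol*

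**What the plan says.** - **Section 2.1, Aim 2**, repeated in the protocol summary: pretreatment variables will be studied to determine "which factors may be associated with sustained virological response and how they may differ between racial groups". Section 8.0 says the ancillary studies are there to reach Aims 2 and 3, so their analysis plans are part of the method for this aim.
- **Section 6.0**: a chi-square test of SVR by race, then logistic regression for "The association between race and SVR after adjusting for potential confounders". Baseline characteristics are also compared between races. The threshold is p<0.05 for all analyses.
- **Section 8.2.2**: because response rates differ by race, the effect of a gene may differ too. "Thus, we will first analyze data separately within each racial group". After that, the races are combined by Mantel-Haenszel or by adjusting for race. Table 10 gives power for the race-stratified Mantel-Haenszel test only.
- **Section 8.2.4**: CD4 power is set out by race, and the CD8 comparison of responders with non-responders is made inside each racial group.
- **Sections 8.2.1 and 8.2.3**: patients are sampled in six groups (race by response pattern), but the stated tests compare races or responder groups one at a time, not crossed.

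The text shown names no race-by-factor term and no test of homogeneity.

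**The concern.** Whether a predictor differs by race is a question about the difference between two associations. A within-race analysis estimates each association. A Mantel-Haenszel or race-adjusted analysis estimates one common association. Neither estimates the difference. Section 8.2.2 raises the possibility of different effects and then fixes a sequence that ends in a common effect, with no check between the two steps that a common effect is reasonable.

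The gap matters because readers will want an answer to Aim 2. If the only material is two sets of within-race p-values, the easy reading is that a factor matters in one race and not in the other. That reading can suggest a racial difference where none exists, and it can miss one where both tests are significant but the effects differ in size.

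**Working it through.** **Inputs from the protocol.** "The study is designed to have 400 patients; 200 White/Caucasian, 200 Black/African American"; SVR 40% and 26%; two-sided alpha 0.05 (all Section 6.0). **Assumptions, because the protocol gives no values:** factor prevalence and within-race odds ratio (OR).

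**1. The plan's own power figure.** Section 6.0 states 80% power for the race comparison. With the logistic sample-size method that the protocol cites for Table 12, and race in standard-deviation units:
- OR = (0.40/0.60)/(0.26/0.74) = 1.897; θ = ln(1.897)/2 = 0.320; mean SVR = 0.33. Required N = 400.4, against 400 planned.
- For 40% vs 25%, N = 347.5. Dividing by 1 − 0.4² = 0.84 for the multiple correlation gives 414, or about 79% power at 400.

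The stated figure reproduces, but for the race effect only. No power is given for a difference in predictors.

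**2. How often separate tests disagree when nothing differs.** For 50% prevalence, each race has 100 patients with the factor and 100 without. SE(log OR) ≈ √[2/(100·p·(1−p))]:
- Caucasian: √[2/(100·0.40·0.60)] = 0.289
- African American: √[2/(100·0.26·0.74)] = 0.322

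Power in each race = P(|Z| > 1.96) with mean ln(OR)/SE. The samples are independent, so disagreement = P_C(1−P_A) + P_A(1−P_C).

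| Common OR | Power, Caucasian | Power, African American | Significant in exactly one race |
|---|---|---|---|
| 1.0 | 5% | 5% | 10% |
| 1.2 | 10% | 9% | 17% |
| 1.5 | 29% | 24% | 39% |
| 2.0 | 67% | 58% | 47% |
| 3.0 | 97% | 93% | 10% |

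Using expected cell counts at each OR instead, OR 2.0 gives power of 66% and 55% and disagreement of 48%. OR 3.0 gives SEs of 0.301 and 0.344, power of 95.4% and 89.2%, and 0.954·0.108 + 0.892·0.046 = 14%.

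**3. What a direct comparison can detect.** SE of the difference in log OR = √(0.289² + 0.322²) = 0.433. The ratio of odds ratios detectable with 80% power is exp(2.80·0.433) = 3.4. With expected cell counts and no effect in African Americans:

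| Prevalence | Detectable ratio, 80% power | Power, OR 2 vs 1 | Power, OR 3 vs 1 |
|---|---|---|---|
| 50% | 3.5 | 36% | 70% |
| 30% | 3.8 | 31% | 64% |
| 10% | 10.5 | 16% | 33% |

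For a continuous factor: SE = √[1/(200·0.40·0.60) + 1/(200·0.26·0.74)] = 0.216, and exp(2.80·0.216) = 1.83 per standard deviation.

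**4. The protocol's own genetics scenarios.** Table 10 includes carrier vs non-carrier response of 0.6 vs 0.4 in Caucasians, OR (0.6/0.4)/(0.4/0.6) = 2.25, together with 0.4 vs 0.1 in African Americans, OR (0.4/0.6)/(0.1/0.9) = 6.0. The ratio is 6.0/2.25 = 2.7. The listed power (0.984, 0.736 and 0.674 at the three significance levels) is for the pooled test, which cannot report that ratio.

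**The case against.** - **The statistical analysis plan is not shown and may add interaction terms.** It may, and silence alone would be no finding. But Section 8.2.2 is not silent: it anticipates different effects and then fixes a sequence that does not compare them.
- **Section 6.0 might be read as imposing race as a main effect only.** The text does not support that. It never says main effects only, speaks of analyses in the plural, lists covariates as examples and checks the fit of the final model. The sentence also serves Aim 1. What stands is narrower: no step there addresses the Aim 2 comparison.
- **A reader might infer that the protocol will declare a racial difference when a factor is significant in one race only.** No section states such a rule, and race-specific estimates can be compared by size and interval. Analysing by race first is also a normal step. The risk lies in what is left for the reader to do.
- **Aim 2 may mean that the levels of the factors differ by race and may explain the SVR gap.** This reading is possible. Section 5.0 asks whether adherence explains the lower SVR, Section 8.2.4 speculates about Th1 frequencies, and Section 6.0 compares baseline characteristics. But the aim speaks of factors associated with SVR, and Section 8.2.2 speaks of effects. If levels are meant, the aim should say so.
- **Interaction tests have low power, and testing every factor at 0.05 would itself create false differences.** Both are true. With 20 independent factors (an assumed number), the chance of at least one false result is 1 − 0.95²⁰ = 64%. This calls for a short list and intervals; it does not justify leaving the comparison out.

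**Conclusion.** The point holds in limited form: followed as written, the stated analyses do not answer the natural reading of Aim 2, and the clearest case is Section 8.2.2. It should be corrected, but it is not a flaw in the primary comparison of SVR by race or in its power.

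The 47% disagreement should not be quoted as a general rate. Disagreement is greatest when within-race power is near one half, and an odds ratio of 2.0 at 50% prevalence lies close to that. Across common odds ratios from 1 to 3 the figure runs from about 10% to about 50%. Prevalence and odds ratio are assumptions; sample size and SVR rates come from Section 6.0. The detectable ratio of about 3.4 to 3.5 is likewise a favourable case, since rarer factors need a larger one. The protocol therefore cannot promise firm conclusions on racial differences in predictors, only estimates with wide intervals.

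**What to change.** - **Section 8.2.2:** add a test of homogeneity of the race-specific odds ratios beside the Mantel-Haenszel analysis, and report both odds ratios. Several Table 10 scenarios have no responders among African American non-carriers, so name an exact version for sparse cells.
- **Section 6.0:** for a short prespecified list of Aim 2 factors, fit race, factor and race-by-factor terms. Report race-specific odds ratios and the ratio of odds ratios with its 95% confidence interval.
- **Both sections:** base any statement that a predictor differs by race on that comparison. Label it exploratory, acknowledge or control multiplicity, and state the limited precision given above.
- **Alternative:** if Aim 2 concerns only differences in factor levels between races, reword the aim in Section 2.1 and in the summary.

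The cost is a few sentences and agreement on the list of factors. No new data or patients are needed.
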